13.3 Analysis of Secondary Endpoints

Secondary outcomes include estimating the incidence of false alerts, the rate of alerts sent out per patient days, characteristics of the patient safety events, and time to response. The analyses of the secondary endpoints will be descriptive and exploratory with the goal of further characterizing the properties of the PUP™ System. Rates and means will be calculated as appropriate. Confidence intervals will be computed to accompany each estimate. No formal statistical testing will be conducted.

We will also examine how fall rates may be associated with patient characteristics. We may also explore data related to the activity level of fall risk patients that are collected by the PUP™ System. These descriptive analyses could help to further characterize the fall risk patient population.

13.4 Sample Size

The primary endpoint of the trial is the patient fall rate per patient days. Comparing to a historical rate of 0.004 using a one-sided test of Poisson means, we have at least 70% power to detect a 25% reduction in the fall rate at alpha level 0.1 with 2360. Assuming a dropout rate of 5%, we will enroll 2500 patients into the study.

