OTHER EVALUATIONS	N/A
SAFETY EVALUATIONS	Incidence of adverse events arising use of device
PLANNED INTERIM ANALYSES	N/A
STATISTICS Primary Analysis Plan	
The primary endpoint for this study is the number of patient falls. This will be expressed as a falls incidence rate, i.e., number of falls per patient days where patient days are counted from the initiation of the PUPTM System until discharge or removal from the fall risk protocol. Using a one-sided one-sample test for Poisson means, we will test whether the observed fall rate is less than the historical rate of 0.004. This test will be conducted at the alpha=0.1 level. Results will be presented as the fall rate and the corresponding one-sided 90% confidence interval which will provide an upper bound for the fall rate.

Rationale for Number of Subjects	The primary endpoint of the trial is the patient fall rate per patient days. Comparing to a historical rate of 0.004 using a one-sided test of Poisson means, we have at least 70% power to detect a 25% reduction in the fall rate at alpha level 0.1 with 2360. Assuming a dropout rate of 5%, we will enroll 2500 patients into the study.
---	---

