4 STUDY DESIGN

4.1 Study Overview

- **Problem** - Falls occur at a rate of 5.5 per 1000 patient days in US hospitals. In addition to the human morbidity and mortality costs, falls cost hospitals in excess of \$8 billion in unreimbursed charges. No intervention to date has been shown to significantly reduce that rate.
- **Purpose** - To determine the effectiveness, if any, of the PUP™ Fall Prevention System. The hypothesis is that the System will reduce the fall rate by at least 25% of prior years' average fall rate.
- **Population to be studied** - All fall risk patients, eighteen years old or older, admitted to OSU Brain and Spine Hospital on Floors 8, 9, and 10 until the sample size is reached.
- **Research Design** – Single arm trial
- **Extent of Researcher Interference** - Minimal, only studying events as they normally occur. The PUP™ System will have been previously evaluated and approved for use as the standard of care at the OSU Medical Center Brain and Spine Hospital in accordance with the terms of an agreement between Palarum and OSU Medical Center dated March 28, 2018.
- **Time horizon** - Current.
- **Study setting** - Non-contrived. OSU Medical Center Brain and Spine Hospital.
- **Measurement and measures**
 - Patient fall rate (measured as number of falls/1000 patient days) data collection and reporting forms, criteria and protocols for the three calendar years preceding initiation of the research.
 - Patient fall rate data collection and reporting forms, criteria, and protocols for the research period calendar year.
 - Data collection standards and protocol for/of;
 - Positive stand detection alert
 - Negative stand detection alert
 - Participant inclusion, exclusion or exemption
 - Sampling methods of 1-3 above
 - Report form(s), structure and content
 - Participant or data exclusion standards, if any.
- **Data Collection Method** - Unobtrusive automated physical measurement using the PUP™ sock, sensors, wireless technology, and REDCap.

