13.2 Analysis of Primary Endpoint

The primary endpoint for this study is the number of patient falls. This will be expressed as a rate per patient days where patient days are counted from the initiations of the PUP™ System until discharge or removal from the fall risk protocol. Using a one-sided one-sample test for Poisson means, we will test whether the observed fall rate is less than the historical rate of 0.004. This test will be conducted at the alpha=0.1 level. Results will be presented as the fall rate and the corresponding one-sided 90% confidence interval which will provide an upper bound for the fall rate.

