## Palarum Data

### Primary dataset

- 732 entries with multiple enrollment and unenrollment dates (technical error)
- 569 patients after data cleaning multiple entries by limiting data to first enrollment and last unenrollment
- Variables included – floor, unit, enrollment date, unenrollment date. From these we calculated length of stay.

Variable	Level	Total (n=569)
OSU unit	Missing	3 (1%)
	10 East	127 (22%)
	10 South	108 (19%)
	8 East	64 (11%)
	8 South	102 (18%)
	9 East	81 (14%)
	9 South	84 (15%)
Length of Stay (Days)	Median [IQR] (min, max)	2 [1, 3.9] (0, 127.2)

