#### Data discrepancies

- There were 58 patients in the OSU data that were not included in the Palarum data
- There were 48 patients in the Palarum data that were not included in the OSU data
- Total of 521 common patients between the 2 datasets

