#### Study Objectives

- To determine if the fall rate (as measured by falls per 1000 patient days) for patients designated “high fall risk” decreases with the use of the intervention (Patient is Up fall prevention technology [PUP]) when compared to historical NDNQI data for the prior 12 months (“Benchmark Data”) from nursing units where the intervention is being undertaken.
  - We ran a one-sided one-sample test for Poisson means using fall events (0 falls) and length of stay (2211.6 days) to estimate the fall rate
  - Results are presented as the fall rate and the corresponding one-sided 90% confidence interval which provides an upper bound for the fall rate.
    - 0 falls (Upper bound 1.04) per 1000 days
  - This fall rate was lower than the historical rate of 4 falls per 1000 days
- To reduce the incidence of false alerts, <5%. Our goal is a high reliability notification system.
  - No data collected for this
- To provide positive alert reliability of 95%. Our goal is to reduce alert fatigue with nurses. To determine number of alerts sent out; what is the frequency of these patient safety events (i.e.), fall risk patient up, out of bed, unassisted
  - No data collected for this
- To gather compliance data and response times from alert to caregiver response.

- Stand Time captured in seconds

Variable	Level	Total (n=4999)
Stand (seconds)	Median (IQR) (min, max)	24.0 (5.0, 64.0) (1.0, 593.0)

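### Does the 70% power claim in Protocol Section 13.4 fail because no length of stay or patient-day total is given?

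*Protocol*

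**What the plan says.** Section 13.4 of the protocol, repeated in the synopsis row on the rationale for the number of subjects, compares the fall rate with a historical 0.004 by a one-sided Poisson test and states: "we have at least 70% power to detect a 25% reduction in the fall rate at alpha level 0.1 with 2360". The next sentence is "Assuming a dropout rate of 5%, we will enroll 2500 patients into the study".

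Section 13.2 defines the endpoint: "This will be expressed as a rate per patient days where patient days are counted from" the start of the PUP System until discharge or removal from the fall risk protocol. Section 4.1 takes patients "admitted to OSU Brain and Spine Hospital on Floors 8, 9, and 10 until the sample size is reached".

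The protocol gives no planned mean stay, patient-day total or expected number of falls. Its only stay figure, 6.3 extra days after a fall (Sections 1.1 and 2), is not a mean stay.

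The SAP describes what was observed. Under Primary dataset it reports "569 patients after data cleaning multiple entries by limiting data to first enrollment and last unenrollment", with a median stay of 2 days. Under Study Objectives it reports the test "using fall events (0 falls) and length of stay (2211.6 days) to estimate the fall rate".

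**The concern.** For a Poisson rate, information comes from exposure time. Two trials of 2360 patients, one with a mean stay of 3 days and the other with 7, have very different power. Section 13.4 nevertheless attaches an unconditional 70% to a bare 2360, and enrolment is tied to a head count. A reader cannot check the figure from the stated inputs. If 2360 were taken as patient-days, the claim would be badly wrong. If it means patients, the claim holds only for a stay that is not written down. At stake would be a trial that recruits to its target and still has less information than its planners believed.

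**Working it through.** **Inputs.** Null rate 0.004 per patient-day, alternative 0.003 (25% lower), one-sided alpha 0.1, size 2360, dropout 5%, enrolment 2500 (Sections 13.2 and 13.4). Total patient-days T is not given.

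**Formulas.**
- Exact test: c is the largest count with P(X ≤ c | 0.004T) ≤ 0.1; power is P(X ≤ c | 0.003T).
- Normal approximation: power = Φ[(0.001T − 1.2816√(0.004T)) / √(0.003T)].

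**Step 1: what 2360 counts.** 2360 / 0.95 = 2484.2, so 2485, rounded up to the stated 2500 patients. The dropout step only makes sense for patients. Read as patient-days, T = 2360 gives c = 5 and exact power 29.1% (normal 27.7%), far from 70%.

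**Step 2: reproduce the 70%.** Try 5 days per patient: T = 2360 × 5 = 11,800.
- Expected falls: 47.2 under the null, 35.4 under the alternative.
- Exact: c = 38, attained alpha 0.0997, power 70.6%.
- Normal: (11.8 − 1.2816 × √47.2) / √35.4 = (11.8 − 8.805) / 5.950 = 0.503, so power is 69.3%.
- The smallest T with exact power of at least 70% is 11,797. Then 11,797 / 5 = 2359.4, which rounds up to 2360.

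A 5-day stay with the exact test therefore returns the plan's own number.

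**Step 3: how firmly 5 days is pinned down.** Mean stay at which 2360 patients give 70% power:

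| Method | Patient-days | Days per patient |
|---|---|---|
| Normal, variance under the alternative only | 9,784 | 4.15 |
| Square-root scale | 11,357 | 4.81 |
| Exact, first reached | 11,797 | 5.00 |
| Normal, null and alternative variance | 12,051 | 5.11 |
| Normal, null variance | 13,046 | 5.53 |
| Log scale | 13,136 | 5.57 |
| Exact, from here on always at least 70% | 13,446 | 5.70 |

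**Step 4: sensitivity to stay (2360 patients).**

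| Mean stay, days | Exact | Normal |
|---|---|---|
| 3 | 53.7% | 52.2% |
| 4 | 59.9% | 61.6% |
| 5 | 70.6% | 69.3% |
| 6 | 73.7% | 75.6% |
| 7 | 80.3% | 80.7% |

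Exact power is saw-toothed: 64.8% at 11,796 patient-days and 70.6% at 11,797. For the same reason 2375 patients (95% of 2500) at 5 days, 11,875 patient-days, show 69.3% exact although they carry more information than 11,800; the normal figure rises from 69.3% to 69.5%. That dip comes from discreteness and is not a shortfall in the design.

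**Step 5: effect on the result.** With 0 falls in 2211.6 days, p = exp(−0.004 × 2211.6) = exp(−8.846) = 0.00014. The one-sided 90% upper bound is −ln(0.1) / 2211.6 = 2.3026 / 2211.6 = 0.00104, or 1.04 per 1000 days, as the SAP reports. Planned power enters neither figure.

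**The case for a change.** The strongest case for a change is that the 70% is stated without condition, yet it depends on a stay nobody disclosed. The SAP's own data suggest a shorter one: 2211.6 / 569 = 3.89 days. At that mean, 2360 patients give 9,173 patient-days and power of 58.6% (exact) or 60.6% (normal). Naming the unit and the assumed stay would cost a few words.

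Part of this stands. The sentence cannot be verified as written, and the 70% is conditional. But the 3.89 days is post-trial information from a much smaller sample, rebuilt from "732 entries with multiple enrollment and unenrollment dates (technical error"). It could not have been a planning input, so it cannot show that the planning was wrong.

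A patient-day target would not be a mere clarification either. Because enrolment stops at the sample size, a binding target would change the stopping rule: 13,446 / 3.89 is about 3,460 patients. A target of 12,050 patient-days would also miss its purpose under the exact test, where power there is 66.1%. The SAP bound of 1.04 agrees with the exact Poisson limit, which suggests that the analysis was exact.

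The SAP's 569 patients against the planned 2500 (22.8%) is a matter of recruitment, separate from the missing stay.

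**Conclusion.** This is a minor reporting omission, and the plan needs no change. Section 13.4 leaves out one input, and a statistician can recover it: about 5 days per patient (4.15 to 5.70 across methods) reproduces the stated 70% with 2360 patients. No arithmetic error is shown.

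The analysis in Section 13.2 does not rely on the missing figure. It uses observed patient-days, so under the Poisson model the exact test holds its level, and the upper bound shows how much information was collected, whatever stay was assumed in planning. Writing the input down would help a reader but would alter no enrolment rule, test or conclusion; the result stays at 0 falls, p = 0.00014, upper bound 1.04 per 1000 days.

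This rests on two assumptions: that 2360 counts patients, which the dropout step supports, and that the planners had a mean stay near 5 days in mind, which is inferred and stated nowhere. If the true planning stay were nearer 4 days, power would have been about 60% to 62% by the exact and usual normal methods, and the 70% would have been optimistic. The documents give no ground for saying that it was.

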14 DATA COLLECTION, RETENTION AND MONITORING

14.1 Data Collection Instruments

The Investigator will prepare and maintain adequate and accurate source documents designed to record all observations and other pertinent data for each subject treated with the study drug.

Study personnel at each site will enter data from source documents corresponding to a subject's visit into the protocol-specific electronic Case Report Form (eCRF) OR paper CRF when the information corresponding to that visit is available. Subjects will not be identified by name in the study database or on any study documents to be collected by the Sponsor (or designee) but will be identified by a site number, subject number, and initials.

If a correction is required for an eCRF, the time and date stamps track the person entering or updating eCRF data and create an electronic audit trail.

The Investigator is responsible for all information collected on subjects enrolled in this study. All data collected during the course of this study must be reviewed and verified for completeness and accuracy by the Investigator. A copy of the CRF will remain at the Investigator's site at the completion of the study.

14.2 Data Management Procedures

The data will be entered into a validated database. The Data Management group will be responsible for data processing, in accordance with procedural documentation. Database lock will occur once quality assurance procedures have been completed.

All procedures for the handling and analysis of data will be conducted using good computing practices meeting FDA guidelines for the handling and analysis of data for clinical trials.

14.3 Data Quality Control and Reporting

After data have been entered into the study database, a system of computerized data validation checks will be implemented and applied to the database on a regular basis. Queries are entered, tracked, and resolved through the EDC system directly. The study database will be updated in accordance with the resolved queries. All changes to the study database will be documented.

14.4 Archival of Data

The database is safeguarded against unauthorized access by established security procedures; appropriate backup copies of the database and related software files will be

maintained. Databases are backed up by the database administrator in conjunction with any updates or changes to the database.

At critical junctures of the protocol (e.g., production of interim reports and final reports), data for analysis is locked and cleaned per established procedures.

14.5 Availability and Retention of Investigational Records

The Investigator must make study data accessible to the monitor, other authorized representatives of the Sponsor (or designee), IRB/IEC, and Regulatory Agency (e.g., FDA) inspectors upon request. A file for each subject must be maintained that includes the signed Informed Consent/HIPAA Authorization Form and copies of all source documentation related to that subject. The Investigator must ensure the reliability and availability of source documents from which the information on the CRF was derived.

All study documents (patient files, signed informed consent forms, copies of CRFs, Study File Notebook, etc.) must be kept secure for a period of two years following marketing of the investigational product or for two years after centers have been notified that the IND has been discontinued. There may be other circumstances for which the Sponsor is required to maintain study records and, therefore, the Sponsor should be contacted prior to removing study records for any reason.

14.6 Monitoring

Monitoring visits will be conducted by representatives of the Sponsor according to the U.S. CFR Title 21 Parts 50, 56, and 312 and ICH Guidelines for GCP (E6). By signing this protocol, the Investigator grants permission to the Sponsor (or designee), and appropriate regulatory authorities to conduct on-site monitoring and/or auditing of all appropriate study documentation.

14.7 Subject Confidentiality

In order to maintain subject confidentiality, only a site number, subject number, and subject initials will identify all study subjects on CRFs and other documentation submitted to the Sponsor. Additional subject confidentiality issues (if applicable) are covered in the Clinical Study Agreement.

15 ADMINISTRATIVE, ETHICAL, REGULATORY CONSIDERATIONS

The study will be conducted according to the Declaration of Helsinki, Protection of Human Volunteers (21 CFR 50), Institutional Review Boards (21 CFR 56), and Obligations of Clinical Investigators (21 CFR 312).

To maintain confidentiality, all laboratory specimens, evaluation forms, reports and other records will be identified by a coded number and initials only. All study records will be kept in a locked file cabinet and code sheets linking a patient's name to a patient identification number will be stored separately in another locked file cabinet. Clinical information will not be released without written permission of the subject, except as necessary for monitoring by the FDA. The Investigator must also comply with all applicable privacy regulations (e.g., Health Insurance Portability and Accountability Act of 1996, EU Data Protection Directive 95/46/EC).

15.1 Protocol Amendments

Protocol amendments cannot be implemented without prior written IRB/IEC approval except as necessary to eliminate immediate safety hazards to patients. A protocol amendment intended to eliminate an apparent immediate hazard to patients may be implemented immediately, provided the IRBs are notified within five working days.

15.2 Institutional Review Boards and Independent Ethics Committees

The protocol and consent form will be reviewed and approved by the IRB/IEC of each participating center prior to study initiation. Serious adverse experiences regardless of causality will be reported to the IRB/IEC in accordance with the standard operating procedures and policies of the IRB/IEC, and the Investigator will keep the IRB/IEC informed as to the progress of the study. The Investigator will obtain assurance of IRB/IEC compliance with regulations.

Any documents that the IRB/IEC may need to fulfill its responsibilities (such as protocol, protocol amendments, Investigator's Brochure, consent forms, information concerning patient recruitment, payment or compensation procedures, or other pertinent information) will be submitted to the IRB/IEC. The IRB/IECs written unconditional approval of the study protocol and the informed consent form will be in the possession of the Investigator before the study is initiated. The IRB/IECs unconditional approval statement will be transmitted by the Investigator to the Sponsor or designee prior to the shipment of study supplies to the site. This approval must refer to the study by exact protocol title and number and should identify the documents reviewed and the date of review.

Protocol and/or informed consent modifications or changes may not be initiated without prior written IRB/IEC approval except when necessary to eliminate immediate hazards to the patients or when the change(s) involves only logistical or administrative aspects of the study. Such modifications will be submitted to the IRB/IEC and written verification that the modification was submitted and subsequently approved should be obtained.

The IRB/IEC must be informed of revisions to other documents originally submitted for review; serious and/or unexpected adverse experiences occurring during the study in accordance with the standard operating procedures and policies of the IRB; new information that may affect adversely the safety of the patients of the conduct of the study; an annual update and/or request for re-approval; and when the study has been completed.

15.3 Informed Consent Form

Informed consent will be obtained in accordance with the Declaration of Helsinki, ICH GCP, US Code of Federal Regulations for Protection of Human Subjects (21 CFR 50.25[a,b], CFR 50.27, and CFR Part 56, Subpart A), the Health Insurance Portability and Accountability Act (HIPAA, if applicable), and local regulations.

The Investigator will prepare a combined informed consent form and HIPAA authorization, and provide the document to the Sponsor or designee for approval prior to submission to the IRB/IEC. The consent form generated by the Investigator must be acceptable to the Sponsor and be approved by the IRB/IEC. The written consent document will embody the elements of informed consent as described in the International Conference on Harmonization and will also comply with local regulations. The

Investigator will send an IRB/IEC-approved copy of the Informed Consent Form to the Sponsor (or designee) for the study file.

A properly executed, written, informed consent will be obtained from each subject and/or LAR prior to entering the subject into the trial. Information should be given in both oral and written form and subjects must be given ample opportunity to inquire about details of the study. A copy of the signed consent form will be given to the subject and the original will be maintained with the subject's records.

15.4 Publications

The preparation and submittal for publication of manuscripts containing the study results shall be in accordance with a process determined by mutual written agreement among the study Sponsor and participating institutions. The publication or presentation of any study results shall comply with all applicable privacy laws, including, but not limited to, the Health Insurance Portability and Accountability Act of 1996.

15.5 Investigator Responsibilities

By signing the Agreement of Investigator form, the Investigator agrees to:

1. Conduct the study in accordance with the protocol and only make changes after notifying the Sponsor (or designee), except when to protect the safety, rights or welfare of subjects.
2. Personally, conduct or supervise the study (or investigation).
3. Ensure that the requirements relating to obtaining informed consent and IRB review and approval meet federal guidelines, as stated in § 21 CFR, parts 50 and 56.
4. Report to the Sponsor or designee any AEs that occur in the course of the study, in accordance with §21 CFR 312.64.
5. Ensure that all associates, colleagues and employees assisting in the conduct of the study are informed about their obligations in meeting the above commitments.
6. Maintain adequate and accurate records in accordance with §21 CFR 312.62 and to make those records available for inspection with the Sponsor (or designee).
7. Ensure that an IRB that complies with the requirements of §21 CFR part 56 will be responsible for initial and continuing review and approval of the clinical study.
8. Promptly report to the IRB and the Sponsor (or designee) all changes in the research activity and all unanticipated problems involving risks to subjects or others (to include amendments and IND safety reports).
9. Seek IRB approval before any changes are made in the research study, except when necessary to eliminate hazards to the patients/subjects.
10. Comply with all other requirements regarding the obligations of clinical investigators and all other pertinent requirements listed in § 21 CFR part 312.

